10.5.6 Abnormal Vital Signs and Other Abnormalities

Not every abnormal vital sign, ECG, or other safety assessment qualifies as an AE. A result must be reported as an AE if it meets any of the following criteria:

 Accompanied by clinical symptoms or lead to a diagnosis (in such case the symptom or diagnosis will be recorded as an AE)

- Results in a change in study treatment (e.g., dosage modification, treatment interruption, or treatment discontinuation)
- Results in a medical intervention, a change in concomitant therapy, or subject referral for further testing outside the protocol
- Clinically significant abnormality in the Investigator's judgement

It is the Investigator's responsibility to review all vital signs, ECG, and other safety findings. Medical and scientific judgement should be exercised in deciding whether an isolated abnormality should be classified as an AE.

If a clinically significant abnormality is a sign of a disease or syndrome (e.g., high blood pressure), only the diagnosis (i.e., hypertension) should be recorded in the eCRF.

Observations of the same clinically significant abnormality from visit to visit should not be repeatedly recorded in the eCRF unless the aetiology changes. The initial severity of the event should be recorded, and the severity or seriousness should be updated any time the event worsens.

10.6 ADR and Reference Safety Information

10.6.1 Adverse Drug Reaction

An ADR is a response to a medical product (any dose administered). A causal relationship between an investigational product and an AE is at least a reasonable possibility. This means that there are facts (evidence) or arguments to suggest a causal relationship.

All AEs judged as having a reasonable causal relationship to an investigational product will be designated as ADRs.

10.6.2 Reference Safety Information

The Reference Safety Information presents the basis for expectedness assessment of an adverse reaction for expedited reporting and annual safety reporting, as well as surveillance of subject's safety in a clinical trial by regulatory (and ethic) bodies.

In the context of this study, the Reference Safety Information is integrated in the latest version of difelikefalin IB.

10.7 Serious Adverse Event

10.7.1 Definition of SAE

An SAE is defined as any untoward medical occurrence that either:

Results in death

- Is life-threatening (the term life-threatening in the definition of serious refers to an event in which the subject was at risk of death at the time of the event; it does not refer to an event which hypothetically might have caused death if it was more severe)
- Requires inpatient hospitalisation or prolongation of existing hospitalisation (unless elective surgery (a planned, non-emergency medical procedure))
- Results in persistent or significant disability/incapacity
- Is a congenital anomaly/birth defect
- Is an important medical event (i.e., medically significant)

Medical and scientific judgement should be exercised in deciding whether expedited reporting is appropriate in other situations, such as important medical events that may not be immediately life-threatening or result in death or hospitalisation but may jeopardise the subject or may require intervention to prevent 1 of the other outcomes listed in the definition above. These events should also be considered as serious.

Any worsening of a pre-existing medical condition or any new medical condition that meets the above SAE criteria should be considered as an SAE.

Any suspected transmission of any infectious agent via a medicinal product should be considered as an important medical event (i.e., medically significant) and therefore documented as an SAE.

The Investigator is encouraged to discuss with the Sponsor (or its delegate, e.g., Contract Research Organisation (CRO)) any AEs for which the issue of seriousness is unclear or questionable.

10.7.1.1 Situations that are Not Considered SAEs

The following situations are not considered as SAEs:

- Visits to the emergency room or hospital department that do not result in a hospital admission lasting more than 24 hours
- Elective or pre-planned surgery for a pre-existing condition that has not worsened
- Routine health assessments requiring admission not associated with any deterioration in condition
- Social admission (lack of housing, family circumstances, etc.)
- A planned overnight stay for logistical reasons only prior to investigational product administration does not fulfil the criteria of an SAE unless there is also a medical reason for the admission

10.7.2 SAE Reporting

The SAE reporting period begins at the time the ICF is signed by the subject. The SAE reporting period ends 30 days following the last study visit or until 30 days after last investigational product administration, whichever is longer. After last study visit, SAEs that comes to the attention of the Investigator must be reported to the CRO/Sponsor and will be documented in the safety database of the Sponsor only and not in eCRF.

A death occurring during the study, or which comes to the attention of the Investigator within 30 days after the last study visit or until 30 days after the last investigational product administration, whichever is longer, whether considered treatment-related or not, must be reported to the Sponsor (or its delegate, e.g., CRO).

Any SAE considered to have a causal relationship (i.e., related) to the investigational product and discovered by the Investigator at any time after the study should be reported. A rationale for the assessment of a causal relationship must be provided by the Investigator. Any safety information that is obtained after database lock of the clinical database will be documented in the safety database and implications for handling the data in the clinical database assessed on an individual case basis.

The occurrence of an SAE must be immediately reported to the Sponsor (or its delegate, e.g., CRO) within 24 hours of awareness using the study-specific Sponsor SAE form/via SAE CRF/eCRF in the electronic data capture (EDC), or as defined in the study monitoring plan. This includes all SAEs (independent of relationship to study treatment).

The onset date of the SAE is defined as the date the signs and symptoms/diagnosis became serious (i.e., met at least 1 of the criteria for seriousness; see Section 10.7.1). If the condition started as a non-serious event and then became serious, 1 AE and 1 SAE will be recorded. The resolution date of the SAE is defined as when the symptoms resolve, or the event is considered chronic (e.g., sequelae) or stable, and/or if the seriousness criteria are no longer applicable.

10.7.3 Suspected Unexpected Serious Adverse Reaction

The definition of a suspected unexpected serious adverse reaction is any ADR (see Section 10.6.1) that is both serious (see Section 10.7.1) and unexpected (per the Reference Safety Information; see Section 10.6.2) that, based on the opinion of the Investigator or Sponsor, is felt to have a reasonable possibility or suspected causal relationship to an investigational product.

10.7.3.1 SAE Expedited Reporting

The Sponsor will notify all Investigators of all SAEs requiring expedited reporting to Regulatory Authorities.

The Investigator is responsible for notifying the Independent Ethics Committee (IEC) in accordance with local regulations of all SAEs that occur. The Investigator must review and file the safety report with the IB.

10.8 Special Situations

10.8.1 Definition of Special Situations

The following are defined as special situations:

- Use of an investigational product during pregnancy or breastfeeding
- Use of an investigational product in a paediatric population
- Medication error: any unintentional error in the prescribing, dispensing or administration of an investigational product during the study
- Medication misuse: an intentional and inappropriate use of an investigational product not in accordance with the protocol dose, route of administration, and/or the indication(s)
- Medication overdose: the administration of a quantity of investigational product given per administration, which is above the protocol maximum permitted dose
- Drug interaction involving investigational product
- Unexpected therapeutic or clinical benefit from investigational product use

Suspected AEs associated with medication errors of the investigational product or use outside that foreseen in the protocol (e.g., overdose,) are also considered as ADRs. Any special situation occurring with/without ADR/AE shall be recorded in the study-specific documentation.

10.8.2 Special Situation Recording and Reporting

All special situations have to be documented in the subject's eCRF and source documents. The Investigator should also complete and submit the Sponsor paper Special Situation form immediately (i.e., within 24 hours of awareness) to the Sponsor, following the same procedure as for SAEs (Section 10.7.2).

If any special situation leads to an SAE (see Section 10.8.1), then the event must be immediately reported to the Sponsor (or its delegate, e.g., CRO) within 24 hours of awareness using the study-specific Sponsor SAE form/via SAE CRF/eCRF in EDC.

10.8.3 Pregnancy Exposure and Birth Events

10.8.3.1 Definition of Pregnancy Exposure and Birth Events

When a female subject becomes pregnant during the study and study treatment has been administered to the subject, the outcome of the pregnancy needs to be monitored and the safety of the mother and unborn child need to be safeguarded (as per-protocol, pregnancy is an exclusion criteria). Therefore, the outcome of all such pregnancies (including normal births) must be followed up and documented, even if the subject was withdrawn from the study or the study has been completed.

Women of childbearing potential, defined as a premenopausal female capable of becoming pregnant, should have a negative serum pregnancy test within 7 days before first dose of investigational product is administered and at the end of study treatment (Day 8). Investigational product should not be initiated by the Investigator until a report of a negative pregnancy test has been obtained. As per inclusion criteria, women of childbearing potential must agree to use adequate contraceptive precautions (e.g., hormonal contraceptives, barrier with spermicide, intrauterine device, vasectomised partner, or abstinence) from the time of informed consent until 7 days after dosing. Please also refer to the eligibility criteria (Section 5).

Per inclusion criteria, male subjects will agree not to donate sperm from investigational product administration until 7 days after the dosing and will agree to use a condom with spermicide or abstain from heterosexual intercourse during the study until 7 days after investigational product administration.

A female subject must immediately inform the Investigator if she becomes pregnant during the study and be instructed to stop taking investigational product. The Investigator should counsel the subject and discuss the risks of continuing with the pregnancy and the possible effects on the foetus.

The Investigator/Sponsor is responsible for monitoring the subject and pregnancy outcome. Every effort should be made to gather information regarding the pregnancy outcome until 90 days postpartum (or otherwise as appropriate). It will be the responsibility of the Sponsor, together with the appropriate support of the Investigator, to obtain this information.

10.8.3.2 Pregnancy Exposure and Birth Events Recording and Reporting

Any report of pregnancy recorded for any female subject or for a female partner of a male subject should be reported to the Sponsor (or its delegate, e.g., CRO) within the same timelines as an SAE, i.e., immediately (within 24 hours of awareness). The outcome of all such pregnancies (including normal births) must be followed up and documented, even if the subject was discontinued from the study. Complications of pregnancy such as abortion (spontaneous or induced), premature birth (before 37 weeks gestational age) or congenital abnormality are considered SAEs and should be reported using the study-specific Sponsor SAE form.

All pregnancies occurring in a female subject or the female partner of a male subject within 90 days after discontinuation of the investigational product should be reported within the same timelines as a SAE to the Sponsor (or its delegate, e.g., CRO).

10.8.4 Adverse Event of Special Interest

10.8.4.1 Definition of AESI

An AESI is a medical occurrence specific to the product or program, for which ongoing monitoring and rapid communication by the Investigator to the Sponsor is appropriate. Such an event, depending on the nature and the outcome, may be serious (see Section 10.7.1) or non-serious.

Based upon results of the studies in the HD population, the following categories (MedDRA PT) were identified as AESIs for the HD population:

- Gait disturbance (gait disturbance)
- Falls (fall)
- Dizziness (dizziness)
- Somnolence (somnolence)
- Seizures (seizure)
- Syncope (syncope)
- Mental status changes (mental status changes)
- Mood changes (mood altered)
- Unusual feeling/sensation (feeling abnormal)
- Tachycardia (sinus tachycardia, tachycardia, and tachyarrhythmia)
- Palpitations (palpitations)

10.8.4.2 **AESI Reporting and Recording**

AEs classified as AESIs will be noted in the AE section of the subject's eCRF and source documentation. Any AESI satisfying any of the criteria for seriousness should be reported using the study-specific Sponsor SAE form/via SAE CRF/eCRF in EDC. The Investigator should notify the Sponsor immediately (i.e., within 24 hours of awareness), following the same procedure as for SAEs (Section 10.7.2).

11. Data and Safety Monitoring Board/Data Monitoring Committee Procedures

An independent Data and Safety Monitoring Board/Data Monitoring Committee will not be used in this open-label study, whose primary objective is to evaluate the PK profile of a single dose (3 times weekly) of difelikefalin in Chinese subjects undergoing HD.

12. STATISTICAL ANALYSIS

12.1 Statistical Methods

All statistical analyses will be performed using SAS Version 9.4 or later (SAS Institute Inc. SAS/STAT, Cary, NC, US) and with WinNonlin® Version 8.3 or higher (Pharsight Corporation, Mountain View, CA, US). Detailed methodology for summary and statistical analyses of the data collected in this trial will be documented in a SAP, which will be finalised prior to study completion. A general description of the planned methods is provided below. Any deviation from the SAP will be noted and explained in the final study report.

Frequency tables for categorical variables (absolutes and relative frequencies) and descriptive statistics for continuous variables (i.e., number of subjects, mean, SD, minimum, median, quartiles, and maximum) will be calculated. All statistical analyses will be purely descriptive.

12.2 Sample Size and Power Calculations

This study will enrol 30 subjects. The sample size for this Phase 1 study is based on a pragmatic approach. No formal sample size calculation has been conducted.

12.3 Randomisation

This is an open-label study, and no randomisation will be applied. Enrolment is defined as the time of signed informed consent.

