4. INVESTIGATIONAL PLAN

4.1 Overall Study Design

This is a Phase 1, single-arm, uncontrolled, open-label study to evaluate the PK, safety, and tolerability of a repeated (3 times weekly) dose of difelikefalin administered as IV bolus injections to adult Chinese HD subjects (Figure 1).

Subjects eligible for the study will receive a unique subject number. Enrolled subjects who terminate their study participation for any reason regardless of whether the investigational product was administered or not, will retain their number. The next subject will be given the next unique subject number.

Enrolled subjects will be administered 0.5 μ g/kg of difelikefalin as a single IV bolus 3 times, within 15 minutes post-dialysis for 1 week. The first dose will be administered on Day 1. The first HD will be the first scheduled dialysis day of the calendar week for the subject (i.e., Monday, or Tuesday).

The schedule of assessments is provided in Table 1.

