5.2 Inclusion Criteria

Subjects are eligible to be included in the study only if all of the following inclusion criteria apply:

- 1. Appropriate written informed consent has been provided by subject or legally acceptable representative. Written informed consent must be provided before any study-specific procedures are performed, including screening procedures.
- 2. Subjects have the ability to understand the requirements of the study, in the Investigator's opinion.
- 3. Chinese subjects aged ≥ 18 to 85 years (inclusive), at the time of consent.
- 4. End-stage renal disease (ESRD) subjects who have been on HD for at least 3 months before enrolment in the study and are currently on HD 3 times per week. Subjects with or without associated pruritus may be enrolled.
- 5. Subjects with a prescription dry body weight between 40 and 100 kg, inclusive.
- 6. If female, is not pregnant, or nursing.
- 7. If female:
 - a. Is surgically sterile; or
 - b. Has been amenorrhoeic for at least 1 year and is over the age of 55 years; or
 - c. Has a negative serum pregnancy test within 7 days before first dose of investigational product, and agrees to use adequate contraceptive precautions (e.g., hormonal contraceptives, barrier with spermicide, intrauterine device, vasectomised partner, or abstinence) from the time of informed consent until 7 days after the last dose of investigational product. Note: If the result from serum pregnancy testing at screening is indeterminate due to possible human chorionic gonadotropin elevation secondary to ESRD unrelated to pregnancy, a serum pregnancy re-test may be repeated prior to treatment Day 1 to establish if a negative result can be confirmed.

8. If male, agrees not to donate sperm from the first dose of investigational product administration (Day 1) until 7 days after last dosing, and agrees to use a condom with spermicide or abstain from heterosexual intercourse during the study until 7 days after the last dose of investigational product. Note: No restrictions are required for a vasectomised male, provided his vasectomy was performed ≥4 months prior to screening.

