5.4 Withdrawal of Subjects

5.4.1 Withdrawal of Subjects from the Study

Subjects may voluntarily withdraw from study participation at any time without having to provide a reason. Subjects may be withdrawn because of the appearance of a new health

condition requiring care or medications prohibited by the protocol, unacceptable AEs, refusal to continue treatment, major non-compliance with study procedures, significant protocol deviations, or at the Investigator's discretion if it is in the subject's best interest.

If a subject withdraws from the study at any time either at his or her request or at the Investigator's discretion, the reason(s) for withdrawal must be recorded on the relevant page of the subject's eCRF and source documentation. Subjects who withdraw from the study prematurely should undergo all end of study assessments, if possible.

If a subject is withdrawn from the study due to an AE, it is vital to obtain follow-up data. In any case, every effort must be made to undertake protocol-specified safety follow-up procedures (see Section 10.3). If a subject is discontinued due to an AE, the event should be followed by the Investigator through contact with the subject until resolution or stabilisation has occurred. All AEs should be followed until resolution, stabilisation, or the subject is lost to follow-up and cannot be contacted.

If a subject refuses to continue study procedures, the reason for refusal should be fully documented in the subject's source document and recorded in the study-specific eCRF. Although subjects are not obliged to give a reason for withdrawing consent, the Investigator should make every effort to obtain the reason, while fully respecting the subject's rights. If the subject withdraws from the trial without providing a reason, the source documents and the eCRF should document the reason for discontinuation as "withdrawal by subject".

Subjects who discontinue from the study after administration of the first dose of investigational product and before completing the protocol procedures will not be replaced.

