6.5 Site Supply, Storage, Accountability

6.5.1 Site Supply

Once a site has been approved to receive investigational product, the site will be supplied with an initial stock of investigational product used in the study. The need for drug resupply will be assessed on a regular basis considering the number of subjects enrolled, and the number of subjects in screening at the site.

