7.2.4 Women of Childbearing Potential

Women of childbearing potential can only be enrolled in the study if:

- They are surgically sterile
- Have been amenorrhoeic for at least 1 year and are over the age of 55 years
- Have a negative serum pregnancy test within 7 days before first dose of investigational product, and agree to use adequate contraceptive precautions (e.g., hormonal contraceptives, barrier with spermicide, intrauterine device, vasectomised partner, or abstinence) from the time of informed consent until 7 days after dosing

Note: If the result from serum pregnancy testing at screening is indeterminate due to possible human chorionic gonadotropin elevation secondary to ESRD unrelated to pregnancy, a serum pregnancy re-test may be repeated prior to treatment Day 1 to establish if a negative result can be confirmed.

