8.1 Allowed Adaptations in Case of Extraordinary Events, e.g., COVID-19

The guidance below is intended for subjects who have been successfully enrolled into the study and who are unable to attend in person clinic visits due to COVID-19 restrictions. Every reasonable effort should be made to ensure that the subject continues on the study per-protocol. Study visits which coincide with dialysis days should be conducted on-site. In the event that a subject cannot come to the clinic after baseline visit due to self-quarantine, local restrictions, or illness, a visit at another local hospital may be considered.

If the subject misses, or is expected to miss, 2 consecutive clinic visits due to COVID-19, the Investigator must contact the Medical Monitor to discuss discontinuation of the subject from the study. In either scenario, the subject should return to the clinic for assessment at their earliest convenience. If it is determined that the subject must be discontinued, the reason for termination should be documented as 'related to COVID-19' under Reason for Termination: Other in the eCRF.

Extraordinary events may call for specific measures to maintain subject safety and guarantee conduct of clinical investigations according to established general and specific guidelines and regulations to meet agreed regulatory, quality, and scientific expectations.

For this, the following adaptations are considered for specific situations:

- Site visits are not possible within the defined time window, possibly leading to delayed visit:
 - On-site monitoring: accept delayed on-site monitoring, conduct remote monitoring.
 - On-site auditing: accept delayed on-site auditing, conduct remote auditing.
 - AE/SAE/special situation reporting: frequent phone call visits.
- Site visits are not possible within the defined time window, possibly leading to no visit:
 - Vital signs: consultation by local physician, follow-up clinical assessment via phone remote visits at subject's home (e.g., home nursing).
 - On-site monitoring: accept delayed on-site monitoring, conduct remote monitoring.
 - On-site auditing: accept delayed on-site auditing, conduct remote auditing.

- AE/SAE/special situation reporting: frequent phone call visits.

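### Does the target of 30 subjects need redefining because enrolment means consent in one section and a later step in others?

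*Combined protocol and SAP*

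**What the plan says.** The synopsis, section 5.1 and section 12.2 give the same size statement: "This study will enrol 30 subjects". Each adds that the number is pragmatic and that no formal calculation was made.

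The only definition of the word is in section 12.3: "Enrolment is defined as the time of signed informed consent". Section 5.2, inclusion criterion 1, places consent first: "Written informed consent must be provided before any study-specific procedures are performed, including screening procedures".

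Other sections use the word for a later step:

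- Section 4.1 opens its dosing sentence with "Enrolled subjects will be administered"; the matching synopsis sentence refers to eligible subjects.
- Section 6.5.1 plans drug resupply by "considering the number of subjects enrolled, and the number of subjects in screening at the site".
- Section 7.2.4 begins "Women of childbearing potential can only be enrolled in the study if" and then lists conditions that include a pregnancy test.
- Section 8.1 addresses "subjects who have been successfully enrolled into the study".

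On replacement, section 5.4.1 says only that subjects who leave "after administration of the first dose of investigational product and before completing the protocol procedures will not be replaced".

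**The concern.** A reader who applies section 12.3 literally would close recruitment at 30 signatures, including people who fail screening or withdraw before Day 1. A reader of section 4.1 would expect 30 dosed subjects. The replacement rule does not decide between them, because it covers only subjects who have already been dosed.

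With no sample size calculation, 30 is the protocol's only commitment on how much pharmacokinetic (PK) and safety data this first Chinese study will produce. If it means consents, the number contributing data could be noticeably smaller, and sites and sponsor could disagree about when recruitment is complete.

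**Working it through.** **No figure to reproduce.** Section 12.2 states that 30 was not calculated. The documents give no screen-failure rate, CV, precision target or minimum number evaluable. The check is therefore a comparison of the text, followed by an illustration on assumed inputs.

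**Step 1: which passages fit the consent definition?**

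| Section | Use of the word | Fits 12.3? |
|---|---|---|
| 4.1, subject numbers | Enrolled subjects who leave keep their number, dosed or not | Yes |
| 12.4.1, safety set | Enrolled subjects with at least one dose | Yes: the dose condition is needed only if enrolled is wider than dosed |
| 12.5, disposition | Enrolled and treated counted separately | Yes |
| 4.1, dosing sentence | Enrolled subjects are dosed | No |
| 7.2.4 | Enrolment depends on sterility, amenorrhoea over age 55, or a negative test | No for the test, which follows consent (section 8.2) |
| 6.5.1 | Enrolled and in screening named separately | Loosely: under 12.3 the second group lies inside the first |
| 8.1 | Successfully enrolled | Loosely: ordinary wording |

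The statistical sections agree with the definition. The clear misfits are the dosing sentence in 4.1 and the test condition in 7.2.4, and neither concerns the count of 30.

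**Step 2: does any analysis depend on the reading?** The safety set (12.4.1) and the PK set (12.4.2) both require dosing. Consent precedes dosing, so every properly dosed subject is enrolled on either reading and the membership rules select the same people. Section 12.1 makes all analyses descriptive, so no error rate is involved. Only the number of people contributing and the enrolled row of the disposition table can differ.

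**Step 3: size, on assumptions.** Let *f* be the proportion of consented subjects lost before the first dose and not replaced. The documents give no value, so 0% to 30% is assumed.

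- Dosed if 30 means consents: 30 × (1 − *f*).
- Consents needed if 30 means dosed: 30 / (1 − *f*), rounded up (30/0.9 = 33.3, 30/0.8 = 37.5, 30/0.7 = 42.9).
- 95% CI factor of a geometric mean: exp[*t*(0.975, *n* − 1) × √ln(1 + CV²) / √*n*], with an assumed CV of 40%.
- Chance of seeing at least one case of an adverse event with an assumed 5% rate: 1 − 0.95^*n*.

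| *f* | Dosed from 30 consents | Consents for 30 dosed | CI factor, CV 40% | P(at least one case) |
|---|---|---|---|---|
| 0% | 30 | 30 | 1.155 | 78.5% |
| 10% | 27 | 34 | 1.165 | 75.0% |
| 20% | 24 | 38 | 1.177 | 70.8% |
| 30% | 21 | 43 | 1.192 | 65.9% |

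From 30 to 24 dosed, the factor goes from 1.077 to 1.087 at an assumed CV of 20%, and from 1.193 to 1.221 at 50%. At 40% the limits move outward by 1.1767/1.1547 = 1.019, about 2%.

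**The case for a change.** The best argument for a change is that a recruitment target governs conduct, and conduct cannot be repaired afterwards. The SAP need only be final before study completion (section 12.1) or database lock (synopsis), which may be after recruitment has closed. An auditor has one explicit definition to apply, and it gives the less favourable count. The same definition supplies the reference date for inclusion criterion 4, the minimum time on haemodialysis before enrolment.

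Part of this stands. The usage is inconsistent, no passage says whether the 30 are consented or dosed, and nothing covers losses before the first dose. Barring replacement specifically after the first dose suggests that earlier losses are handled differently, but it does not say so.

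The step from there to a needed change does not stand. Closing at 30 consents would miss no stated requirement, because none exists beyond the 30 itself. The possible gain is a few more dosed subjects, obtained by screening more people. Redefining enrolment as confirmed eligibility would also have side effects. It could move the reference date in criterion 4 by up to the three-week screening period. It would also alter the safety set, which is restricted to enrolled subjects: someone dosed without confirmed eligibility could drop out of it unless section 12.4.1 were rewritten too.

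**Conclusion.** No change to the plan follows. This is loose wording around a definition that the protocol does state and that its statistical sections follow. The sponsor can settle operationally when to stop recruiting, and the separate enrolled and treated counts in section 12.5 will show how many subjects were dosed.

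The consequence is limited to precision. If 30 means consents and pre-dose losses are not replaced, an assumed loss of 10% to 30% leaves 27 to 21 dosed subjects. At an assumed CV of 40%, the CI factor rises from 1.155 to between 1.165 and 1.192. No analysis set rule, summary or conclusion depends on which reading is used. The loss rates, CV and 5% event rate are all assumptions. The conclusion itself rests on the descriptive purpose and the absence of a precision target; had 30 come from a power or precision calculation, what it counts would have mattered.
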